Respiratory cycle-related EEG changes (RCREC) will be computed as previously described. Briefly, a central EEG lead and airflow from a thermocouple signal are analyzed. Signals from computer-detected regions of apnea or hypopnea (generally a small minority of the total recording time) are excluded. Remaining respiratory cycle airflow signals are smoothed and divided into quarters (early expiration, late expiration, early inspiration, and late inspiration); EEG spectral power within pre-determined frequency ranges of interest are computed by digital filtering; and the mean power for each quarter-cycle, relative to power over the entire respiratory cycle, is computed. Results for each quarter-cycle segment are averaged over thousands of respiratory cycles (generally several hours of recording) and the maximal difference between mean relative segment powers is defined, for any given subject and within the targeted EEG frequency band, as the RCREC value. The investigators have shown that RCREC are greater in children with SDB than those without SDB;

RCREC improve after adenotonsillectomy; they correlate with subjective and objective measures of sleepiness in children and adults; this association persists after accounting for objective measures of SDB severity; RCREC correlates with esophageal pressure swings but is far from completely explained by them; and RCREC may well reflect subtle but numerous cortical microarousals in response to labored non-apneic breathing that pervades much of the night for patients with SDB. In the research now proposed, sigma range (12-15 Hz) RCREC will be the main focus, as RCREC within this range have proved most sensitive to sleepiness in both adults and children.

Esophageal pressure swings for all respiratory cycles, after exclusion of irregular breaths and artifacts, will be computed automatically using an algorithm developed by the investigators and previously shown to match well with much more time-consuming visual analyses. Sleep dynamics analyses will involve computation of the mean lengths of contiguous sleep and specific sleep stage bouts. The investigators have previously shown that these data may characterize sleep fragmentation more sensitively, in children with SDB, adults with fibromyalgia, or adults with asthma, than do arousals or standard analyses of sleep stages as total minutes, percentages of total sleep time, or sleep efficiency.

**C5. Neurobehavioral Assessments.** Standardized, well-validated tests will be used to assess outcomes widely recognized as some of the most important and sensitive in childhood SDB. As noted above, many studies of SDB morbidity have found associations with inattentive, hyperactive, and aggressive behavior, and with cognitive problems such as attention deficit. Behavioral and cognitive measures, confirmed to be useful in our previous studies of childhood SDB and in related work by our group and others, will provide outcomes for this study. Validated parental rating scales for inattention, hyperactivity, general behavioral issues, and quality of life will best assess the primary complaints parents often communicate and clinicians seek to address. Other outcomes will include neuropsychological measures of short-term attention, visuospatial problem solving, executive functioning, and memory. These measures are important for assessment of cognitive changes in treated and untreated patients with sleep disorders, as well as attention deficit and other medical disorders, and many are available in multiple, equated forms to reduce practice effects. General intelligence and academic achievement will be briefly assessed, because in some reports they are sensitive to SDB and because they should be taken into account when other specific outcomes are analyzed. Although the investigators have in previous research on AT included psychiatric evaluations, these are now omitted because AT effectively reduces the rates of DSM-IV diagnoses to a level that would be difficult to study without an enormous postoperative sample. In contrast, continuous measures provided postoperatively by parental behavior rating scales, cognitive assessments, and Multiple Sleep Latency Tests do not reach levels identical to those of controls and should be more sensitive to benefits from CPAP after AT.

**Behavioral Assessments:** Standardized rating scales to be completed by a child's parent or guardian will include the Conners' Parent Rating Scales (CPRS-R:L) and the Child Behavior Checklist (CBCL), with the primary study outcome measure, Behavioral Index, being constructed from the sum of the T-scores from the Conners' ADHD Index and CBCL Attention Deficit/Hyperactivity Problems. Parents also will complete the CPRS-R:L and CBCL at the pre-operative meeting after signing the consent materials with their child. Although not representing a primary outcome point for this study, this assessment will serve to familiarize parents with the process of observational reporting on their child; provide important information or grouping variables for secondary analyses; and help to confirm that CPAP and control groups have equivalent behavior at baseline. Because of the importance consistently reported for the measurement of executive functioning in children with SDB, the Behavior Rating Inventory of Executive Functioning (BRIEF) also will be completed. Finally, quality of life will be measured from both the Peds-QL parent and child forms. The CPRS-R:L, CBCL, and BRIEF are available in teacher forms that will allow secondary, corroborative assessment in both a home and school environment, and help address any evident parental bias. Through experience in our laboratory and work with the multicenter Childhood Adenotonsillectomy (CHAT) trial, for which our center directs quality assurance and monitoring of behavioral and cognitive assessments, we have developed techniques to sustain strong return rates for teacher ratings.

Any or all survey instruments used in this study may be administered as paper forms or electronic versions, which may be delivered by email or via a web-based software system such as Qualtrics, or as a combination of paper and pencil and electronic formats, depending on the form type and the reporter (child, parent or teacher). *Any instrument for survey over the internet will be or is being developed through the auspices of the computer*

*support group in Psychiatry and MCIT to be sure it is HIPPA compliant, as are current measures employed in Psychiatry for their patient metrics.*

**Cognitive Assessments.** Tests will be administered by an experienced, neuropsychologist-supervised psychometrist who is well trained to maintain children's motivation and monitor the need for rest breaks or changes in conditions. Each child also will receive a brief introduction to face-to-face testing using CogState (described below) during the time just following consent signing. As many children will not have had the experience of being tested before, this introduction will reduce apprehension and familiarize each child with the types of materials to be tested. The total testing time for post-AT sessions will be approximately 2 hours, spread between nap studies. This is less time than routine clinical evaluations (usually 4-8 hours). All specific test sessions will occur at the same time of day, without variance between subjects or test and retest visits.

The Attention/Executive Functions domain score of the NEPSY-II and the computerized continuous performance test, Integrated Variables of Attention, will comprehensively cover short term and sustained attention, vigilance, impulsivity, and executive ability. Overall intelligence and academic achievement will be assessed briefly using the two Stanford-Binet, 5th Edition (SB5) "routing tests", Matrices and Vocabulary and selected Woodcock Johnson-III subtests (Letter Word Identification, Reading Fluency, Calculation, and Applied Problems). The Selective Reminding Test is sensitive to children's memory, specifically verbal encoding and retrieval. Speed and control of fine motor ability will be measured with the Purdue Pegboard. Finally, the brief computerized CogState battery will provide valid indices of processing speed, working memory, executive functioning, and memory in a combined measure that remains stable over time, incorporates simple response requirements and self-contained training modules, and has proven inherently interesting and motivating, and sensitive to subtle cognitive change in children. This test also includes the Groton Maze Test, a brief, computerized measure of psychomotor speed and visuospatial problem solving.

As newer versions of these or other equivalent neurobehavioral tests are released, they may be substituted for currently available versions, as deemed necessary by the PI and CoInvestigators on the project to meet the project aims. For example, an equivalent battery of neurobehavioral and quality of life measures has been developed as part of a NIH Toolbox for the Assessment of Neurological and Behavioral Function and is expected to become available in the near future. Because the NIH toolbox battery spans ages 3-85 and is designed to minimize subject burden, components of this battery may be substituted, whenever appropriate, on this study.

**C6. Intervention.** All CPAP group participants will have a CPAP titration study shortly after the initial post-AT polysomnogram. During this additional night in the sleep laboratory, pediatric core technologists will fit each child with an appropriate mask, monitor sleep and breathing as above, and remotely increase administered pressures until SDB resolves. Each record will be scored as above, but by any available registered pediatric sleep technologist (not waiting for batching) so that an investigator ([name]) can promptly review the study and determine an ideal pressure setting to prescribe. An experienced respiratory therapist at MedEQUIP will then meet with the family, issue them a CPAP machine and mask at no cost to the family, educate them about CPAP use, and serve as a contact should any mechanical problems arise.

Approximately every 30 days (or more often as necessary) over the next 6 months, the DME provider or study team staff will review compliance data that is remotely downloaded via modems on the PAP machines. Alternatively, data downloads may also be done onsite from the SD memory cards in the PAP machines. Adherence and therapeutic data will be stored in a secure office of Encore Anywhere, a HIPAA compliant, web-based patient compliance management system provided by Philips Respironics, the manufacturer of the PAP machines used on this protocol. Restricted access to Encore Anywhere "offices" is provided by Philips Respironics, and the offices are password protected. The study data files will be maintained in a separate office from the UMHS clinical patient compliance database in Encore Anywhere. This will restrict casual access to the research data by other UM providers or staff. Linkable identifiers will be used in the place of subject names to help maintain privacy for research participants.

Detailed plans to promote adherence, to be elaborated in the operations manual, will include phone calls approximately weekly for the first 3 weeks to detect any problems early; a meeting with the study nurse or

other investigators at 3 months; additional meetings or phone interviews every 4-6 weeks; further intervention of [name] (research assistant and experienced pediatric sleep clinic nurse) as needed; and referral to [name] (co-investigator and psychologist in Pediatric Sleep and Behavior Clinic) when adherence is problematic. *All no-CPAP group participants will receive a series of contacts from an investigator, to control for this potential confound (see Introduction), including an interval visit with the study nurse or other investigators between study visits 2 and 4, whenever possible; assistance with referral at the end of the study for any desired or indicated clinical follow-up; and research-funded PAP equipment if a child without insurance coverage requires treatment. A brief 7-items survey will be administered to children and parents (both arms of the study) at the interval (~3month followup) clinic visit with study staff and again at the endpoint visit to elicit additional information on their experience or health status during their participation. Copies of the survey are available in the Manual of Procedures.*

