Note that Addendum #1 provides for enrollment of subjects after adenotonsillectomy at or prior to study visit 2. This allows increased opportunity for interested families who are not able to schedule the pre-operative visit or who are referred to the study after their surgery to participate in this research. More information on this additional study arm is provided in the addendum and the MOP.

**C3. Procedures.** Each participant will undergo a baseline, pre-randomization evaluation of sleep and neurobehavioral variables at 4 months after AT, as several months are required to ensure complete healing. Most of the neurobehavioral benefit achieved after AT for SDB accrues in the first 3 months (unpublished data from the investigators). After baseline assessments, all subjects will be randomized to CPAP or non-CPAP (standard care) groups. Group assignments will be made using a randomization algorithm, possibly with automatic adjustment that prospectively ensures balance between groups for SDB status, residual post-operative SDB symptoms, gender, age and/or BMI. Non-CPAP families will be contacted by the program manager for 6 months at intervals designed to replicate the frequency and nature of investigator contacts in the CPAP group. Discussion will focus on recuperation after AT, general health, and any suggestion of serious adverse effects that would warrant discontinuation of study participation and referral for clinical evaluation. These end-points would include recommendations by a child's pediatrician or otolaryngologist to pursue this option; development of a new, serious cardiopulmonary condition that makes prompt assessment and treatment for any residual SDB imperative; or emergence of serious academic or developmental concerns in the setting of obvious, persistent symptoms of SDB. Each questionable case will be brought by the program manager to the PI (section 6.5) for a decision and possible notification of the DSMB per the Data and Safety Management Plan guidelines.

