An unmasked, board-certified sleep specialist will interpret each sleep study, not to provide study variables but rather to inform families and their physicians. Study results generally will not be communicated until after the participant has finished the entire protocol, when sleep and psychological test results are fully scored. However, an investigator will promptly communicate any finding that could have medically urgent significance for the patient, such as an unsuspected arrhythmia, paroxysmal EEG spikes, or severe residual SDB.

Nocturnal polysomnograms and Multiple Sleep Latency Tests will be scored by a single chief technologist ([name], RPSGT, REEGT) masked to subject identity. This technologist has meticulously scored about 1,000 pediatric sleep research studies in the past 10 years. Borderline polysomnographic features will be arbitrated between the technician and the PI. Scoring will be performed in batches: pre- and post-PAP studies of 5 subjects will be randomly ordered and presented for scoring. This procedure, used for two past R01s, assures that any subtle changes in scoring tendencies over time do not confound pre- vs. post-PAP comparisons. Scoring for sleep stages, respiratory events, periodic leg movements, and arousals will follow standard criteria for children. Double-scoring of arousals and respiratory events, in 20% of the records, will be performed to generate a Kappa statistic for intra-rater reliability. Inter-rater reliability will also be determined by having another experienced polysomnographic technologist score these same records.

For Multiple Sleep Latency Tests, the sleep latency of each nap will be scored as the time between lights out and the first epoch of stage 1 sleep. The mean sleep latency across naps is the most well-validated and commonly used objective measure of daytime sleepiness in both adults and children. Childhood sleepiness as a continuous variable for research purposes can be detected in SDB patients as young as 3 years old by questionnaires and by Multiple Sleep Latency Tests.

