### **(c) Exploratory Outcome Measures:**

Measures of academic achievement, fluid cognition, and REREC are all considered exploratory.

C8. Analyses. For Hypothesis 1a, post-AT SDB as an outcome variable will be defined as a respiratory disturbance index (RDI)  $\geq 1$  obstructive or mixed apnea, hypopnea, or respiratory effort-related arousal per hour of sleep. The 22-item SDB scale score (on a continuous scale from 0.0 to 1.0^43) will provide the main explanatory variable. Logistic regression models will be assessed for sensitivity to potential covariates or confounds, including age, gender, race, body mass index z-score, and socioeconomic status. Secondary analyses will focus on RDI as a continuous outcome; validated snoring, sleepiness, and behavior subscales within the SDB scale; habitual snoring as a single, previously informative question-item; and most importantly SDB data generated by innovative algorithms, as described above, exploratory analyses for RCREC, esophageal pressures, and sleep dynamics. For Hypothesis 1b, multiple linear regression models will be constructed to assess cross-sectional associations between each neurobehavioral morbidity (the Behavioral Index being the primary outcome) and the SDB questionnaire score or RDI as the main explanatory variable. Models of the SDB questionnaire will use a slightly shortened, 16-item version (as previously) to exclude behavioral questions that would correlate with outcome measures for artificial reasons. Covariates as above will be taken into account. Secondary analyses will 1) assess the impact of SDB scores or RDI on other behavioral and cognitive measures; 2) take IQ and achievement into account within the main models; and 3) test the 3 newer, computed SDB measures in place of RDI. To assess Hypothesis 2a, the investigators will define adequate adherence as at least 4 hours of electronically recorded CPAP use per night, on average over the most recent 3 months on treatment. A series of multiple linear regression models will be used, with post-CPAP improvement in neurobehavioral variables as outcomes. The pre-CPAP SDB questionnaire scores or RDI will serve as the main explanatory variables. Secondary analyses will use the 3 SDB measures generated by computer algorithms as the explanatory variables. To assess Hypothesis 2b, the same outcomes will be regressed on CPAP adherent vs. non-adherent categorization, as well as (secondarily) a continuous measure of adherence as defined by mean hours of nightly use during the last 3 months of the trial. As with Hypotheses 1a and 1b, models for 2a and 2b also will be assessed after adjustment for similar potential covariates or confounds. To assess Hypothesis 2c, intent-to-treat analyses will use models that regress each primary neurobehavioral outcome on initial CPAP vs. control group assignment, after adjustment for BMI z-scores, age,

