Some children in this protocol will use PAP without having enough underlying, residual SDB to benefit from the intervention. During the treatment trial, neither investigators nor families will know who these children are. Although symptoms may be readily apparent, sleep study results will not be available until after study participation is complete, for several reasons. One is that sleep studies are to be scored in batches -- with several subjects’ pre-PAP and post-PAP studies all in the same de-identified batch -- to avoid any influence of scoring drift over time. A second reason is that at present, knowledge about how post-AT care should be guided by sleep study results remains quite limited. The research now proposed, in fact, aims in large part to address this void.

Fortunately, subjects without residual SDB after AT, as compared to subjects with SDB, have no known additional risks to use of PAP. When the PAP titration studies are performed, children without SDB will have normal breathing, technologists will have no reason to test more than the lowest CPAP settings, and the reviewing physician (co-investigator [name]) can be expected to assign the lowest settings for use at home. In other studies of adults, even CPAP at fixed pressure settings for all research subjects, whether healthy or ill, has been safe whether SDB is present or absent.

Families whose children have been randomized to the control group will be contacted by the program manager during the 6-month trial at intervals designed to replicate the frequency of investigator contacts in the CPAP group. Discussion will focus on recuperation after AT, general health, and also any suggestion of serious adverse effects that would warrant discontinuation of study participation and referral for clinical evaluation. These end-points would include recommendation by a child’s pediatrician or otolaryngologist to pursue this option; development of a new, serious cardiopulmonary condition that makes prompt assessment and treatment for any residual SDB imperative; or emergence of serious academic or developmental concerns in the setting of obvious, persistent symptoms of SDB. Each questionable case will be brought by the program manager to the PI and, depending on the nature of the event as outlined in the Data and Safety Management Plan, the DSMB(section 6.5 below) for a decision.

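### The sleep-disordered breathing factors that may be balanced at randomization need a definition available at that time, and the primary H2c model should include whichever factors are used

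*Combined protocol and SAP*

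**What the plan says.** **Allocation (C3).** The wording is conditional: "Group assignments will be made using a randomization algorithm, possibly with automatic adjustment that prospectively ensures balance between groups for SDB status". In full, the optional adjustment is one that "prospectively ensures balance between groups for SDB status, residual post-operative SDB symptoms, gender, age and/or BMI". SDB status stands apart from symptoms but is not defined, and no balancing method is named.

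**Scoring (C4).** Study scores come from one masked technologist working in batches: "pre- and post-PAP studies of 5 subjects will be randomly ordered and presented for scoring". There is also a separate clinical read: "An unmasked, board-certified sleep specialist will interpret each sleep study, not to provide study variables but rather to inform families and their physicians". Urgent findings, including severe residual SDB, are passed on promptly.

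**Availability (6.2.b).** Of children who use PAP without enough residual SDB to benefit, the plan says: "During the treatment trial, neither investigators nor families will know who these children are". It adds that "sleep study results will not be available until after study participation is complete".

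**Pre-randomization withdrawal (6.1.c).** Children whose apnea at SV2 is too severe for equipoise leave the study before randomization.

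**Primary model (C8, H2c).** The models "regress each primary neurobehavioral outcome on initial CPAP vs. control group assignment, after adjustment for BMI z-scores, age", followed by gender, race and socioeconomic status. The respiratory disturbance index (RDI) and the questionnaire score enter only exploratory models.

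**Questionnaire (C2, C3, C8).** The SDB score is reassessed at 4 months before randomization, with a positive cut-off above 0.33. It exists in a 22-item form and a 16-item form without the behavioral questions.

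**The concern.** Two things do not fit together.

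First, an allocation algorithm can use only what is known when the child is randomized. If SDB status means the masked score, that score does not exist until about six months later.

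Second, the other listed balancing factors (gender, age, BMI) are all in the H2c model, but the two SDB factors are not. Balancing on a prognostic factor lowers the true variance of the treatment estimate. A model without the factor still counts its variation as noise, so the reported standard error is too large and the test rejects less often than it should.

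H2c carries the trial's only primary outcome, so its allocation and model should be settled in the text. What is at stake is clarity about who sees SV2 findings and when, plus a modest amount of power. Validity is not at stake.

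**Working it through.** **1. Timing.**
- SV2 sleep study: about 4 months after surgery. Randomization follows the baseline assessments.
- SV4 sleep study: about 6 months after randomization.
- Masked scoring: SV2 and SV4 studies share a batch, so no masked SV2 score can precede SV4.
- Questionnaire score, gender, age and BMI: all available at SV2.
- Some SV2 severity judgment: needed before randomization by 6.1.c. C4 provides an unmasked read but says it does not supply study variables. No section says when it is done or whether it may feed allocation.

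**2. The plan's own power figure (C9).** Inputs: 80 CPAP and 40 control children, effect 0.55 SD, alpha 0.05. C9 gives alpha under H1a and does not state sidedness; two-sided is assumed.
- SE = √(1/80 + 1/40) = 0.1936, and 0.55/0.1936 = 2.840.
- Normal approximation: Φ(2.840 − 1.96) = 0.811. Noncentral t: 0.804.
- One-sided would give 0.884. The stated 80% is therefore two-sided and uses no covariates.

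**3. Omitting a balanced factor.** Let r be the partial correlation of the SDB factor with Behavioral Index change, given the covariates already in the model, and f = √(1 − r²). Under the normal approximation with exact balance:
- Balanced, not in model: power = Φ((2.840 − 1.96)/f); true size = 2(1 − Φ(1.96/f)).
- In model: power = Φ(2.840/f − 1.96); size 0.05.

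| r (assumed) | f | Power, balanced only | True size, balanced only | Power, adjusted | Difference |
|---|---|---|---|---|---|
| 0.2 | 0.980 | 81.5% | 0.045 | 82.6% | 1.1 points |
| 0.3 | 0.954 | 82.2% | 0.040 | 84.6% | 2.4 points |
| 0.4 | 0.917 | 83.2% | 0.033 | 87.3% | 4.1 points |

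Example, r = 0.3: 0.880/0.954 = 0.923, Φ = 0.822; 2.840/0.954 − 1.96 = 1.017, Φ = 0.846 (unrounded inputs).

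**4. Simulation check** (20,000 runs, a two-level SDB factor split 60/60, 2:1 allocation within level).
- r² = 0.0625, balanced: size 0.042 and power 0.814 unadjusted; power 0.831 adjusted.
- r² = 0.25, balanced: size 0.023 and power 0.835 unadjusted; power 0.900 adjusted.
- r² = 0.0625, no balancing: size 0.048 and power 0.804 unadjusted; power 0.827 adjusted. Adjustment helps whether or not balancing is used.

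**5. Chance imbalance without balancing.** With residual SDB in 47% to 66% of children (C10.3), the SD of the between-arm difference in prevalence is √(p(1 − p)(1/80 + 1/40)), or 9.2 to 9.7 points. A gap above 10 points arises by chance in about 28% to 30% of trials.

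**The case against.** The strongest reply is that the plan promises very little here. C3 makes balancing optional and ends its list with and/or, so no factor is committed to. A reader might infer that randomization will balance on SDB status; the text does not say so.

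A reader might also infer that such balance is impossible. That holds only for the masked score. SDB status is undefined, an unmasked read of each study exists, and 6.1.c needs some view of SV2 severity before randomization.

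A third tempting reading is that the whole precision gain is thrown away, with power rising from 80% to 82%, 84% or 87% once the score is added. Those figures (noncentral t, same correlations) start from no balance and no covariates. If balance is achieved, part of the gain is already kept, and omission costs about 1, 2 or 4 points.

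Nor do the documents show that the SDB factors are the most prognostic ones listed. The Specific Aims and A3 doubt consistent or linear links between standard sleep-study measures and behavior. H2a concerns response among adherent CPAP users, which is not prognosis in both arms. On the other side, C10.2 reports that the questionnaire predicted hyperactivity and its response to surgery.

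Finally, C8 already plans exploratory models with RDI and questionnaire scores. These aim to explain outcome differences and may use 10-month values, so they do not replace a baseline covariate in the primary model.

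What stands: the undefined SDB status, the unreconciled sections, and the missing SDB terms in the primary model.

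**Conclusion.** The point holds as a low-cost improvement. The masked SV2 score cannot serve in allocation, and C3, C4, 6.1.c and 6.2.b do not agree on who sees SV2 findings and when. The H2c model leaves out both SDB factors that allocation may use.

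If they are used and are prognostic, the test is mildly conservative: true size about 0.045 to 0.033, and a power cost of about 1 to 4 points, for assumed partial correlations of 0.2 to 0.4. The documents give no such correlation. The nearest figure, 0.25 in C9, is a detectable cross-sectional association for H1b and not an estimate for change scores. At r² = 0.01 the cost is well under one point (0.812 against 0.814).

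A reader might infer a biased or underpowered primary test. Neither follows: type I error is not inflated, and the stated 80% reproduces with no covariates at all.

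**What to change.** **C3.** State whether balancing is used, by what method and on which factors. Define the SDB factor by something available before randomization: for example the SV2 SDB questionnaire score, or a named unmasked read with a rule on who may see it and pass it to the allocation system. Otherwise delete SDB status from the list. Reconcile C3, C4, 6.1.c and 6.2.b on access to SV2 findings.

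**C8.** Include in the primary H2c model every balancing factor actually used. In any case add the SV2 questionnaire score as a continuous baseline covariate, since splitting it at 0.33 would weaken its correlation with the outcome. State whether the 22-item or 16-item version is meant; for H1b, C8 uses the shorter one because the behavioral questions overlap with the outcomes. SV2 RDI can be added as a further baseline covariate once scored.

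**Cost.** Wording in C3 and C8, and the reconciliation of C4, 6.1.c and 6.2.b. The questionnaire and sleep-study data are already collected, and the sample size is unchanged.
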